9.6. Data Management

The processes for database management will differ per country. In general, data are stored at the database level and analysed locally. The SAS Software will be used to access the raw data, manage the analytic datasets and compute data analysis.

Each database complies with local regulations in terms of data protection and record retention. The study will follow relevant chapters of European Network of Centres for Pharmacoepidemiology and Pharmacovigilance (ENCePP) and International Conference of Harmonisation ICH guidelines for data management.

Data will be checked in terms of consistency before data analysis. This is mainly due to the fact that the record of information in EHR databases is not controlled (unlike case report forms). Thus the data needs to be checked for consistency in terms of range of values, units of measurement, relevance of clinical information (for example, pregnancy for men). Some data providers, such as IMS Health, have already integrated these checks in their data production workflow, so that the checks are conducted systematically on all incoming patient records before allowing them to be integrated into the database.

9.7. Data Analysis

9.7.1. General Statistical Considerations

The analysis will be performed per country, on the overall data set of eligible patients and per subpopulations.

Data coming from different databases/countries will not be pooled due to the difference between structure of panels of health care professionals who contribute the data, asynchronicity of databases, heterogeneity in data structure, coding, and prescribing practices. The analysis will be done per year, and will not be cumulative. Thus data coming from different years will not be pooled either.

The statistical analysis will be descriptive including standard univariate analysis; no inferential statistical analyses will be conducted. Continuous variables will be described by the number of available values, mean, standard deviation, median, Q1, Q3, minimum and maximum. Data not available in the databases will be reported as missing. Categorical variables will be described as the total number of available values and relative percentage per subgroup of interest. When relevant, 95% confidence intervals will be calculated for the endpoints.

The statistical analysis will be conducted using the SAS[®] software V9.2 or later on Windows[™] (SAS Institute, North Carolina, USA).

9.7.2. Subgroups and Outcomes/Measurements Analysed to Answer the Endpoints

Analyses will be performed in the 9 subgroups of interest (See Section 9.2.3).

9.7.3. Sensitivity Analyses

A sensitivity analysis will be conducted for the calculation of off-label use. For this variable, the definition of patients with T2DM will be considered based on the criteria from variables sections. However, for the following criteria two ranges of age will be analysed, once at age>30 and <50 and the other at age>50. Both results will be presented in the study and then discussed.

- ATC codes A10A initiated at age>30
- ICD-10 codes E14 first recorded at age>30 without ATC code A10A in the previous 6 months

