9.3. Variables

Regardless of the coding system used in the database, different populations and subgroups of interest are defined as follows:

Treatment initiation with dulaglutide:

- any record of prescription of dulaglutide during the observation period without prior record of prescription of the same product in the available patient's history
- if no prior history is available to check the above criteria, the prescription is not considered as an initiation

Patients presenting with T2DM:

- with any recorded diagnosis code for T2DM
- or with any recorded treatment code for an ADM other than insulin
- or, with any recorded treatment code for insulin initiated at age >30 (defined as no record of insulin therapy during 6 months prior to first record of insulin treatment)
- or with any record of unspecified diabetes mellitus diagnosis at age >30 and without history of insulin therapy (defined as no record of insulin therapy during 6 months prior to first record of diabetes diagnosis),
- a sensitivity analysis will be conducted to determine the age threshold mentioned above (see section 9.7.3 Sensitivity analysis).

Patients with severe renal failure:

- with a recorded diagnosis of severe renal failure
- or with a recorded glomerular filtration rate (eGFR) value <30 ml/min/1.73 m²

Patients with hepatic disease:

- with a recorded diagnosis of any hepatic disorder

Patients with heart failure:

- with a recorded diagnosis of heart failure

Patients with severe gastrointestinal disease:

- with a recorded diagnosis of any of the following conditions:
 - cancer of the gastrointestinal tract,
 - diseases of the oesophagus,
 - active ulcer at the time of drug initiation (gastric, duodenal, gastro-jejunal, peptic ulcer of unspecified site),
 - active haemorrhagic gastritis, chronic atrophic gastritis, adult hypertrophic pyloric stenosis, obstruction of duodenum, and other motility disorders,
 - digestive fistula,
 - Crohn's disease, ulcerative colitis,
 - diverticular disease of the intestine,
 - severe vomiting, severe diarrhoea and severe constipation
 - motility disorders, including ileus, gastroparesis, et cetera,
 - infectious and inflammatory situations (appendicitis, cholecystitis, cholangitis).

Children and adolescents:

- Age < 18 at the time of treatment initiation
(subgroups of analysis: 0-4, 5-9, 10-14, and 15-17 years old).

Elderly:

- Age \geq 75 at the time of treatment initiation.

Pregnant and breastfeeding women:

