- Any record of pregnancy or breast feeding at the time of treatment initiation.

Patients with medication errors:

- Prescribed and/or administered > 1 dose per week of dulaglutide (6).
- The number of doses/week will be calculated by measuring the time span between the current prescription and the next one (in weeks) and dividing the number of injections prescribed in the current prescription by this time span. This number of doses/week will be used in the cross sectional study as an attribute of the prescription to assess the occurrence of medication errors as described above.

Patients with off-label use:

- Prescribed dulaglutide with no diagnosis of T2DM as defined above, at the beginning of this list of subgroups of populations.
- Prescribed dulaglutide with a diagnosis of T2DM as defined above and without a record of other ADMs during the 6-month baseline period, i.e. dulaglutide was prescribed as first-line therapy.

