
Other comorbidities frequent in T2DM patients: Dyslipidemia Hypertension
 
Macrovascular complications: Ischaemic heart disease
 
Stroke Peripheral arterial obstructive disease
 
Microvascular complications: Diabetic neuropathy Diabetic retinopathy Diabetic nephropathy
	
ICD-10 codes E78 or lipid modifying agents (ATC C10) ICD-10 codes I10-I15 or antihypertensives (ATC C02, C03, C04, C07, C08, C09) with no angina pectoris (I20, I25)
 
ICD-10 codes I20-I25 or antiangina agents (ACT C01D, C07, C08, C09) I61-I64 I70.2
 
G62.9 H36.0 N08.3

Solid tumours (Cancer)
 
 • liver • pancreas • endometrium • colon • rectum • breast • bladder 	
ICD-10 codes C220-C229 ICD-10 codes C250-C259 ICD-10 code C541 ICD-10 codes C182-C189 ICD-10 code C20 ICD-10 codes C500-C509 ICD-10 codes C670-C679

Dulaglutide dose: per 0.5 ml
	
Dose: 0.75 mg / week 1.5 mg / week >1.5 mg / week

Variables, Subgroups and Measurements of Interest

Variable, subgroup or outcome/measurement	Definition and categories*
Concomitant medications for T2DM , at index date of dulaglutide initiation	
 • Molecule: INN/brand name • ATC code or associated medcode for AMD 
A10A Insulins and analogues
 
 ○ A10AB Insulins and analogues for injection, fast-acting ○ A10AC Insulins and analogues for injection, intermediate-acting ○ A10AD Insulins and analogues for injection, intermediate- or long-acting combined with fast-acting ○ A10AE Insulins and analogues for injection, long-acting ○ A10AF Insulins and analogues for inhalation 
A10B Blood glucose lowering drugs, excluding insulins
 
 ○ A10BA Biguanides ○ A10BB Sulfonylureas ○ A10BD Combinations of oral blood glucose lowering drugs ○ A10BF Alpha glucosidase inhibitors ○ A10BG Thiazolidinediones ○ A10BH Dipeptidyl peptidase 4 (DPP-4) inhibitors ○ A10BX Other blood glucose lowering drugs (exenatide, liraglutide, lixisenatide, albiglutide), excluding insulins 
A10P SGLT2 Inhibitors

Other concomitant medications , at index date of dulaglutide initiation	
 • ATC codes or associated medcode for main pharmacological classes.
History of medications for T2DM , during 6-month baseline period	
 • ATC code or associated medcode for anti-diabetes medications (see above)

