History of other medications , during 6-month baseline period	
 • ATC code or associated medcode for main pharmacological classes.
Off-Label Use	
 • Patients without T2DM • Patients with T2DM for whom dulaglutide was prescribed as first-line therapy

Variable, subgroup or outcome/measurement	Definition and categories*
T2DM	Any of the below conditions: 
 • ICD-10 code E11 • ATC codes A10P or A10X • ATC codes A10A initiated at age>30 • ICD-10 codes E14 first recorded at age>30 without ATC code A10A in the previous 6 months

Abbreviations: ALT= alanine amino transferase; AST= aspartate amino transferase; Beta hCG=Beta subunit of human chorionic gonadotrophin; BMI= body mass index; eGFR= estimated glomular filtration rate; HDL-C= high density lipoprotein cholesterol; ICD-10= International classification of disease, 10th version; LDL-C= low density lipoprotein cholesterol; T2DM= type 2 diabetes mellitus; UK= United Kingdom.

* continuous variables will be also presented by means, SD, et cetera.

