9.9. Limitations of the Research Methods

9.9.1. *Limitations Related to Specific Databases*

The main limitations are related to the variables availability in the databases used to answer the study objectives:

- Data reported in the French and German DA are collected through GPs. Nevertheless, a proportion of dulaglutide prescriptions will be initiated by specialists and renewed by the GP. Some patients treated with dulaglutide will probably be followed-up only by a specialist and not be present in DA databases. Consequently, the number of patients initiated could be lower than expected in these databases.
- Some variables will not be reported for all patients by the physicians (it depends on physicians' willingness and the usefulness of the variable for clinical practice).
- The disease diagnosis will be missing for some patients or not correctly reported, especially at primary care level. Codes to identify antidiabetic treatments will be used to compensate for this under reporting of diagnoses for diabetic patients for example.
- The identification of the disease severity is very limited in the databases; it is necessary to define diagnosis via ICD-10 codes (DA, registry data).
- Lab values are not available for all patients in all databases.
- Lab values (for example, HbA1C) and risk factors (for example, BMI, blood pressure, cholesterol level) are not available in the Swedish health registers, but would be available in EHRs.
- Pregnancy (via ICD-10) information is very limited in the French and German DA.
- Data about breastfeeding are very limited in the databases.
- The number of doses administered per week is not known in SIDIAP. The number of doses dispensed in retail pharmacies can be estimated, but it needs to be considered as a proxy measure of administered doses.

- The SIDIAP database does not include information about diabetes history.
- The SIDIAP database includes only data from patients collected in the Catalonia region, and will not be representative of all T2DM patients in Spain.

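### Any non-insulin antidiabetic record, including metformin or another GLP-1 RA, counts as T2DM without a diagnosis; this can only lower the 'without T2DM' count, and no sensitivity analysis tests it

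*Protocol*

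**What the plan says.** Protocol Section 9.3 classes a patient as having T2DM on any one of four criteria joined by 'or'. The second is "or with any recorded treatment code for an ADM other than insulin". It requires no diagnosis and sets no age limit or time window.

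The same section defines off-label use by two limbs. The first is "Prescribed dulaglutide with no diagnosis of T2DM as defined above", referring back to that list. The second is T2DM so defined, with no other antidiabetic drug recorded in the 6-month baseline (first-line use). The mock table in Section 9.7.4 reports the two limbs in separate rows.

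The T2DM row of Table 9.3.2-1 (Section 9.3.2) gives the codes for the non-insulin criterion as "ATC codes A10P or A10X". Elsewhere that table lists "A10BA Biguanides", "A10BX Other blood glucose lowering drugs (exenatide, liraglutide, lixisenatide, albiglutide), excluding insulins" and "A10P SGLT2 Inhibitors".

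Section 9.7.3 keeps the T2DM definition and changes only the age range for two criteria, insulin (A10A) and unspecified diabetes (E14): "However, for the following criteria two ranges of age will be analysed, once at age>30 and <50 and the other at age>50".

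Section 9.9.1 explains why treatment codes are used: "Codes to identify antidiabetic treatments will be used to compensate for this under reporting of diagnoses". The only direction of error it gives for off-label use is an overestimate of first-line use.

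**The concern.** The study asks whether one GLP-1 RA is prescribed to people without T2DM. Under the Section 9.3 text, a record of another GLP-1 RA, or of metformin, is itself enough to place a patient inside the indication. If a GLP-1 RA prescription can be off-label, a second one is not safe proof of the indication.

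The error introduced by this rule goes one way. It can move a patient out of 'without T2DM', but never into it. Off-label use is a named subgroup of the primary objective, and the secondary objective describes it within each population of interest, so both inherit the error. A reader of Section 9.9.1 would expect off-label figures to err high, whereas this row errs low because of the rule.

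**Working it through.** The plan gives no figure for this misclassification, so the check is to apply the rules to one type of patient: no diabetes diagnosis, no insulin, and at most one kind of other antidiabetic record (metformin or another GLP-1 RA). I assume that dulaglutide's own prescription is not counted as the qualifying record. If it were, every initiator would have T2DM and the first limb would be empty.

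**Step 1. Classification by timing of the record**

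| Metformin or other GLP-1 RA record | Section 9.3 text | Table 9.3.2-1 codes, literally |
|---|---|---|
| In the 6-month baseline | T2DM, not first-line: **on-label** | Off-label, without T2DM |
| Older than 6 months | T2DM: off-label, first-line | Off-label, without T2DM |
| Only at index | T2DM: off-label, first-line | Off-label, without T2DM |
| None | Off-label, without T2DM | Off-label, without T2DM |

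Under the text, the first three patients all leave the 'without T2DM' row. Only the first leaves the off-label total. Under the table codes none of them moves, because A10BA and A10BX are not listed. The two definitions therefore classify the same patient differently.

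**Step 2. What Section 9.7.3 can detect**

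Because the four criteria are alternatives, a patient who meets the non-insulin criterion has T2DM whatever age range is set for the other two. Changing the age can reclassify only patients with neither an E11 code nor a non-insulin antidiabetic record. The patients in Step 1 with a record are unaffected.

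**Step 3. Illustrative size**

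The inputs are assumptions and are not in the documents: q is the true share of initiators without T2DM, and f is the fraction of them with a metformin or other GLP-1 RA record at any time.

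Reported 'without T2DM' = q × (1 − f). Per 1000 initiators:

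| q | f = 0 | f = 0.25 | f = 0.5 | f = 0.75 |
|---|---|---|---|---|
| 2% | 20 | 15 | 10 | 5 |
| 5% | 50 | 37.5 | 25 | 12.5 |
| 10% | 100 | 75 | 50 | 25 |

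The relative shortfall in the row equals f, so the table shows how the error scales and is not evidence of its size.

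The loss from total off-label use is q × b, where b ≤ f is the fraction with a baseline record. At q = 5% and f = 0.5 it lies between 0 (all records older or at index) and 25 per 1000 (all in the baseline).

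**Step 4. Comparison with sampling error**

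Half-width = 1.96 × √(p(1 − p)/n), the formula of Section 9.5.1 solved for precision. It agrees with the plan at p = 50%: 9.8 points at n = 100 and 3.1 points at n = 1000, against the stated 10% and 3%. At p = 5%:

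- n = 1000: 1.96 × √(0.0475/1000) = 1.35 points
- n = 100: 1.96 × √(0.0475/100) = 4.27 points

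An undercount of 2.5 points (q = 5%, f = 0.5) exceeds the first and is smaller than the second. Countries are not pooled, so which comparison applies depends on each country's count.

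**The case against.** **The proxy is deliberate and explained.** Section 9.9.1 says that diagnoses will be missing and that treatment codes are meant to make up for this. It also has a general misclassification paragraph saying such errors cannot be checked. This stands: the disclosure is wider than the first-line overestimate alone. What is missing is the direction for the 'without T2DM' row.

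**The table may not apply the proxy to these drugs at all.** Read literally, its codes leave metformin and other GLP-1 RAs out. This stands as a contradiction, but it does not settle the matter: the off-label definition points to the list in Section 9.3, while Section 9.7.3 words its criteria in the table's codes.

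**A reader might infer that all dulaglutide use for weight, prediabetes or polycystic ovary syndrome is counted as on-label.** The documents do not support this. They name none of these uses, and patients whose other record is older or only at index remain off-label as first-line. Patients with no such record remain 'without T2DM'.

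**A stricter definition has its own error.** The Swedish patient register covers specialist and hospital care, while the drug register covers all dispensing, so a true T2DM patient treated in primary care with metformin may have no code. SIDIAP is said to lack diabetes history. This stands, and it is why the stricter definition should be shown beside the present one and not replace it.

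**The SAP could add it.** Possibly, but Section 9.7.3 already fixes the sensitivity analysis for off-label use, and the SAP is to be based on the protocol.

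**Conclusion.** The point holds under the Section 9.3 text. Any error that the non-insulin criterion causes in 'without T2DM' is downward, whatever the timing of the record. Total off-label use is lowered only through baseline records; older or index-only records shift patients to the first-line row, which rises. Section 9.7.3 cannot reveal either effect, and Section 9.9.1 does not give the direction.

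The size is unknown from the documents. A reader might infer a shortfall of some particular percentage, but any such figure only repeats the assumed fraction with a record. Nor does it follow that the row is too low overall: uncoded T2DM patients with no other drug record would push it up, and that is a separate error.

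The conflict between Section 9.3 and Table 9.3.2-1 needs no assumption. The two definitions give different answers for the same patient, and until they are reconciled the off-label count is not uniquely defined.

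**What to change.** 1. Reconcile the non-insulin criterion in Section 9.3 with the codes in the T2DM row of Table 9.3.2-1, so that the text and codes name the same drugs.

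2. Add to Section 9.7.3 a second T2DM definition in which metformin alone, or another GLP-1 RA alone, does not establish T2DM when there is no diabetes code, no other antidiabetic class and no insulin. State how a patient with both is handled.

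3. Report both off-label limbs and their total, by country, under both definitions. With respect to this proxy, the Section 9.3 definition gives the lower bound and the stricter one the upper bound for 'without T2DM' and for the total. The first-line row moves the other way, because patients with only older or index records leave it.

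4. State in Section 9.9.1 that the treatment-code criterion can only lower the 'without T2DM' row.

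The cost is one further sensitivity analysis on diagnoses and drug classes that are already to be extracted. The drawback is that the upper bound includes uncoded T2DM patients and may be wide where primary-care diagnoses are not captured, as in Sweden. The report should say so beside the figures.

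### The first age range in the off-label sensitivity analysis caps age at 50 instead of moving the threshold, so patients aged 50 or over who qualify as T2DM only through insulin start or unspecified diabetes become non-T2DM in that run

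*Protocol*

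**What the plan says.** The T2DM definition in Protocol section 9.3 is a list of alternatives, any one of which is enough. Two do not depend on age: "with any recorded diagnosis code for T2DM" and "or with any recorded treatment code for an ADM other than insulin". The other two infer T2DM from insulin started, or unspecified diabetes recorded, after age 30. Neither has an upper age limit. The same list then states that "a sensitivity analysis will be conducted to determine the age threshold mentioned above" and points to section 9.7.3.

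Section 9.7.3 opens with "A sensitivity analysis will be conducted for the calculation of off-label use". It keeps the general definition but, for two criteria, says that "two ranges of age will be analysed, once at age>30 and <50 and the other at age>50". The criteria are "ATC codes A10A initiated at age>30" and "ICD-10 codes E14 first recorded at age>30 without ATC code A10A in the previous 6 months". Both results are to be presented and discussed.

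Off-label use (section 9.3, and Table 9.3.2-1 in section 9.3.2) has two components: dulaglutide prescribed without T2DM as defined, and dulaglutide prescribed in T2DM with no other anti-diabetes medication (ADM) in the 6-month baseline, which counts as first-line use. Table 9.3.2-1 gives the non-insulin drug route to T2DM more narrowly than the text, as "ATC codes A10P or A10X".

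**The concern.** Testing a threshold means moving the lower cut-off and seeing how the result responds. The first range leaves the lower cut-off at 30 and adds an upper limit that appears nowhere else in the protocol. The base rule treats later onset as evidence for T2DM, yet this run rejects the latest starters and keeps the younger ones.

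This is the only sensitivity analysis in section 9.7.3. Off-label use is a subgroup under the primary objective and the whole of the secondary objective. Section 9.9.1 says that treatment codes are meant to make up for under-recorded diabetes diagnoses. In Sweden the patient register covers specialist and hospital care (section 9.4.3), so diagnoses made only in primary care may be missing. The inferred routes may therefore carry some weight. If so, one of the two planned results would show a classification effect that readers would take for uncertainty about off-label use.

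**Working it through.** The plan gives no figure for this analysis, so there is none to reproduce. The check applies the rules to patient profiles and then bounds the effect.

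**Step 1: the rules.** For the insulin (A10A) and unspecified-diabetes (E14) criteria:
- Main rule: age >30.
- Run A: age >30 and <50.
- Run B: age >50.
- Comparison rule: open-ended ≥50.

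The other two criteria apply unchanged in every run. Dulaglutide itself is not counted as a qualifying drug. (Taken literally, the section 9.3 text would count it, and then nobody would be without T2DM in any run. That is a separate defect, which the Table 9.3.2-1 code list does not share.)

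**Step 2: classified as T2DM?**

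| Qualifying record | Main | Run A | Run B | ≥50 |
|---|---|---|---|---|
| Insulin only, age 40 | yes | yes | no | no |
| Insulin only, age 50 | yes | no | no | yes |
| Insulin only, age 60 | yes | no | yes | yes |
| E14 only, age 60 | yes | no | yes | yes |
| Insulin at 60 plus E11 | yes | yes | yes | yes |
| Insulin at 60 plus metformin, section 9.3 text | yes | yes | yes | yes |
| Insulin at 60 plus metformin, Table 9.3.2-1 codes | yes | no | yes | yes |

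Run B behaves as a raised threshold should: only patients at or below the new cut-off lose the T2DM label. Run A removes the label from patients at the other end of the age range. A patient aged exactly 50 fails both runs.

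**Step 3: effect on off-label use.** Take a patient who loses the T2DM label in run A.
- No ADM in the baseline: under the main rule the patient is already off-label as first-line use. Run A moves the patient to the without-T2DM row, and total off-label use does not change.
- An ADM in the baseline: under the main rule the patient is not off-label. Run A makes the patient off-label, and the total rises. Under the section 9.3 text this ADM must be insulin, because any non-insulin ADM would itself establish T2DM. Under the table's codes it could also be metformin, which the same table lists under A10BA and not under A10P or A10X.

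**Step 4: size.** Let
- q = share of initiators who are T2DM only through A10A or E14,
- s = share of those whose qualifying records all date from age 50 or later,
- b = share of those reclassified who have an ADM in the baseline.

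Rise in the without-T2DM component = q × s.
Rise in total off-label use = q × s × b, which is at most q × s.

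The documents give none of the three. With s assumed to be 0.5 to 0.9:

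| q (assumed) | q × s |
|---|---|
| 1% | 0.01 × 0.5 to 0.01 × 0.9 = 0.5 to 0.9 points |
| 5% | 0.05 × 0.5 to 0.05 × 0.9 = 2.5 to 4.5 points |
| 10% | 0.10 × 0.5 to 0.10 × 0.9 = 5 to 9 points |

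These are ceilings for total off-label use, reached only if b = 1. If b = 0 the total does not move and only the split between the two rows changes.

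**The case against.** The strongest defence is that the ranges are age strata: patients inferred to have T2DM are displayed by age at insulin start or first record, and nobody is reclassified. The wording about analysing ranges leaves some room for this. But section 9.7.3 attaches the ranges to the criteria that define T2DM and restricts no denominator, and strata would still not test the threshold that section 9.3 names. The sentence needs rewriting on either reading.

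It may also be said that the statistical analysis plan will settle the matter. Section 9.7.5 bases that plan on the protocol, and the protocol has already fixed the ranges. This is a mis-stated rule, not a detail left for later.

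Other parts of the defence stand. The main analysis at >30 is unaffected, the study is descriptive, and the capped range would be visible to a careful reader.

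A reader might infer more than the documents support:
- That every insulin starter over 50 becomes off-label. The definition is a list of alternatives, so an E11 code or another qualifying drug code keeps the patient in T2DM.
- That both ranges are faulty. The second is open-ended and fails only in leaving out age 50.
- That total off-label use rises by the full q × s. First-line patients are already counted.
- That the runs are wrong because they do not bracket the main result. Any stricter cut-off can only remove patients from T2DM, so the thresholds proposed below would not bracket it either.

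**Conclusion.** The point holds in a limited form. Section 9.7.3 does not carry out the threshold analysis that section 9.3 announces. As written, its first range classifies as without T2DM those patients aged 50 or over who qualify solely through insulin start or unspecified diabetes, and age exactly 50 is lost from both runs. The fault lies in the first range and in the gap at 50.

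Total off-label use in that run is inflated only through sole-route patients who had an ADM, such as insulin, in the baseline period. The ceiling of q × s rests on assumed values of q and s. The effect could be negligible if nearly all initiators carry a T2DM code or another qualifying drug code, and several points if many do not. The documents do not show which case applies, so no single figure should be quoted. The correction should be made before data are extracted.

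**What to change.** In section 9.7.3, replace the two ranges with open-ended alternative thresholds, applied to both the A10A and the E14 criterion: main >30 and alternative ≥50, neither with an upper limit. An intermediate cut-off such as >40 is optional. Report off-label use under each threshold, split into without T2DM and first-line use, so that movement between the two rows can be told apart from a change in the total. The mock table (Table 9.7.4-1) already has both rows.

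If a display by age stratum is also wanted, describe it separately and state its denominator.

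The cost is one rewritten sentence and the same programming with different limits. No additional data are needed.
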